### 5.3 Tolerability and Safety Objectives

To evaluate the local and general tolerability of DermoRelizema ecofoam.

## 6. Design of the Clinical Investigation

### 6.1 General

This is a multicenter, open label, uncontrolled, post-market clinical follow-up investigation.

All the subjects will be allocated to the following treatment group:

- DermoRelizema ecofoam, topically applied twice a day in all the affected areas for 42 consecutive days.

The subject will start treatment on the first day of study and will go on until 42 days after the first application. The treatment could be prolonged or shortened of maximum 2 days, in the case intermediate and/or final visits are delayed.

Each subject for whom written consent is obtained will be identified during the study by a "Subject Code", automatically generated and assigned by the e-CRF.

All screened subjects will receive the Code regardless of whether they receive the treatment or not. If a subject discontinues from the study at any time, the Code will not be re-used.

All subjects who will sign the informed consent and receive the Subject Code will be entered into a Subject's Register, containing the name and surname of the patients and their Subject Codes. The Subject's Register will be accessible for source data verification but will be preserved only at clinical site.

Once eligibility of a patient is established (see Inclusion/Exclusion Criteria) the study treatment will be assigned.

The Investigator will keep record of all enrolled patients in the Subject's Screening/Enrolment Log: the Subject Code, the date of consent, the treatment assigned to the patient, if applicable, or the reason for not actively entering the study will be recorded.

## **6.2 *Investigational device***

### **6.2.1 *DermoRelizema ecofoam***

The product under investigation is DermoRelizema ecofoam.

Manufacturer:	Relife Srl, [name]
Device Name:	DLP034
Trade Name:	DermoRelizema ecofoam
Formulation:	ecofoam
Route of administration:	topical application on breached/compromised skin
Composition:	aqua, peg-40 hydrogenated castor oil, glycerin, betaine, pullulan, capryloyl/ caproyl methyl glucamide, sodium cocoyl glycinate, ethylhexylglycerin, panthenol, propylene glycol, tocopheryl acetate, lauroyl/ myristoyl methyl glucamide, glycetyl caprylate, chondrus crispus powder, sodium butyroyl/formoyl hyaluronate, sodium

hyaluronate, hexamidine diisethionate, biotin, caprylhydroxamic acid, citric acid.

It is formulated without fragrances, paraben, alcohol and gas. Nickel, antimony, arsenic, cadmium, cobalt, chrome, mercury and lead tested.

DermoRelizema ecofoam is a CE marked, Class IIa medical device, dermatological compact mousse for topical use indicated for symptomatic treatment of all types of dermatitis (including atopic dermatitis, contact dermatitis, or dermatitis caused by radiotherapy and solar radiation) and erythema. It forms a thin protective layer on the skin which protects against external irritants, without hindering normal perspiration, and helps reduce redness. Additionally, due to its light texture, it can also be easily applied to large areas.

#### *6.2.1.1 Packaging and labelling*

DermoRelizema ecofoam will be provided for the study by the Sponsor of this clinical investigation. The study product shipment to the study sites will be done only after the completion of all Ethics and Administrative procedures.

The product will be labeled as experimental treatment in accordance with applicable Good Manufacturing Practice (GMP, Annex 13).

The primary package is a 70 ml labelled canister with pump. Each subject will receive a total of no. 3 canisters and he/she will use a variable amount of cream depending on the extent of the area/s affected by dermatitis to be treated. Occasionally, if the subject needs further treatment (beyond the 3 canisters received), the Investigator will be able to provide further amount of treatment. Additional canisters provided to the subject will be recorded in the CRF.

#### *6.2.1.2 Study device instructions for use*

Patients will be instructed to use DermoRelizema ecofoam two times daily: the first application in the morning and the second in the evening before bedtime, for 42 consecutive days.

At the first use of the product the patient should be instructed to press the valve two or three times to activate the pump mechanism. After this, the subject should press the valve gently to obtain one or more doses of the product to apply on the selected area and massage.

#### *6.2.1.3 Handling and storage*

It is the Investigator/Institution's responsibility to set up a system for handling the clinical investigation treatment, so as to ensure that:

- deliveries of product supply from the Sponsor are correctly received
- products are handled and stored safely and properly in a secured area
- treatments are only dispensed to study subjects in accordance with the clinical investigation plan
- any unused, used, partially used product is returned to the Investigator (including empty canisters).

The study product shall be carefully stored at the study site, in a safe area and separately from other devices/drugs/products. It shall be stored in a dry and cool place, away from direct sunlight or heat.

The pharmacist and/or the Investigator shall maintain records of the study products receipt by the study site and an updated inventory of the study product.

Treatments will be dispensed to the subjects enrolled in this clinical investigation only by authorized personnel.

After study conclusion, all unused study product shall be returned to the Sponsor or destroyed at site after written Sponsor approval.

#### *6.2.1.4 Study product accountability and compliance*

The Investigator is responsible for ensuring the accountability of the study product.

Accountability records will include:

- confirmation of product delivery and receipt to/at the clinical site
- records concerning the product delivery to each subject and the return from each subject
- the return to the Sponsor or alternative disposition of unused products.

The Investigator should maintain records that adequately document:

- that the subjects were provided with the quantities specified by the clinical investigation plan/amendment(s)
- that all study products provided by the Sponsor were fully reconciled.

Unused products must not be discarded or used for any purpose other than the present clinical investigation.

Products that have been allocated to one subject must not be re-dispensed to a different patient.

Subjects will be reminded of the importance of strictly complying with the instructions received from the Investigator and to return all unused treatment or empty canisters to the Investigator.

The Investigator will check and register when subjects are bringing back to the site the used/unused products. Compliance to the treatment will be done with subject's diary information.

### 6.2.2 *Concomitant Medications/Treatments*

Any medications (other than those excluded by the clinical investigation plan) that were considered necessary for the patients' well-being and do not interfere with the study product can be given at the Investigator's discretion.

According to exclusion criteria, the following prior and concomitant medications are prohibited:

- any topical product for dermatitis
- oral antihistamines and antidepressants
- corticosteroids (by any route)
- antibiotics
- immunosuppressant drugs and immunotherapies
- any systemic treatment or procedure that could influence dermatitis
- chemo and radiotherapies
- sun exposure or tanning booths or UV sources.

The subject will be recommended not to use any other product for the personal hygiene than the one provided by the Investigator.

Any concomitant medication/treatment shall be recorded in the appropriate section of the CRF.

## 6.3 *Subjects*

In this clinical investigation 40 subjects will be enrolled fulfilling the following eligibility criteria.

### 6.3.1 *Inclusion criteria*

1. Subject's written informed consent obtained prior to any study-related procedures;
2. Generally healthy male and female aged  $\geq 18$  years;
3. Presence of dermatitis of any typology, including atopic dermatitis (AD), irritant contact dermatitis (ICD) or allergic contact dermatitis (ACD), of mild-moderate severity:
  - IGA score 2 (=mild) or 3 (=moderate)
4. Dermatitis affecting one or more body areas (face, legs, arms, etc.);
5. Subjects with cooperative attitude, able to comprehend the full nature and the purpose of the investigation, including possible risks and side effects, and able to comply with the requirements of the entire investigation (including ability to attend the planned visits according to the time limits), based on Investigator's judgement.

### 6.3.2 *Exclusion criteria*

1. Severe dermatitis at inclusion;
2. Pregnant and breastfeeding women;
3. Concomitant other skin disorders including skin infections;
4. Currently or previously diagnosed or treated (chemotherapy and/or radiotherapy) for cancer in the past 5 years;
5. History of previous skin cancer (history of non-metastatic squamous or basal cell carcinoma of the skin is allowed);
6. Active infections or use of antibiotics in the past 7 days;
7. Diabetic subjects;
8. History of congenital or acquired immunodepression;
9. Immunologic or infectious disease (e.g. hepatitis, tuberculosis, HIV or AIDS, any typology of lupus, rheumatoid arthritis) which could place the subject at risk or interfere with study results;
10. Use of any topical medication for dermatitis in the past 14 days;
11. Use of any topical product for dermatitis in the 2 days before study treatment start;
12. Any systemic treatment or procedure that could influence dermatitis activity within the past 30 days (or 5 half-lives);
13. Use of any corticosteroids, immunosuppressant drugs or immunotherapy within the past 30 days (or 5 half-lives);
14. Use of oral antihistamines and antidepressants in the past 30 days;
15. Subjects with any other clinically significant or unstable concurrent disease or skin condition or general condition that, in the Investigator's opinion, might interfere with the study evaluations;
16. Allergy, sensitivity or intolerance to the components of the investigational device formulations ingredients;
17. Concomitant or previous participation in other interventional clinical study in the past 3 months;
18. Subjects planning sun exposure or tanning booths or UV sources throughout the course of the study.

## 6.4 Procedures

### 6.4.1 Study Visits and Assessments

#### Visit 1 screening – baseline- treatment start (day 1):

Subjects will be evaluated with regard to the inclusion and exclusion criteria that will allow their participation into the study.

Before any study specific evaluation is carried out, subjects will receive all the information about the study by the Investigators and will sign an informed consent form.

The following activities will be performed:

- Collection of information about demography
- Medical and surgical history
- Physical examination, focused on skin examination
- IGA on dermatitis
- EASI Score
- Previous (in the 30 days before) and concomitant medications/treatments recording
- Inclusion/exclusion criteria assessment
- VAS for pain, itching, burning, pruritus
- DLQI questionnaire
- Study product delivery to subject and instructions on how to use it
- Recommendations for personal hygiene to follow
- Diary dispensation and explanations on how to fill it in.

Diary: on the diary each subject will record, at the end of each day, the study product applications performed.

**Recommendations for personal hygiene to follow:** throughout the treatment phase subjects will be required to avoid soap and use only the product DermoRelizema liporestitutive cleanser, particularly indicated for dry and sensitive skin, provided by the Investigator for bathing and showering (bathing should be once a daily, with warm water, for approximately 5 to 10 minutes).

**DermoRelizema ecofoam application:** to apply the study product on the affected body areas twice per day, once in the morning and once in the evening before bedtime. No additional creams, moisturizers, lotions or cleansers other than the product provided by the Investigator will be permitted.

Visit 2 (Day 14 ± 1) and Visit 3 (Day 28 ± 1) – follow-up visits:

The following activities will be done at Visit 2 and Visit 3:

- Physical examination, focused on skin examination
- IGA on dermatitis
- EASI Score
- Change in concomitant medications/treatments recording
- VAS for itching, burning, pain, pruritus
- DQLI questionnaire
- Diary compilation check with the subject for treatment adherence and collection
- New diary delivery
- Study product collection and accountability
- New product delivery
- Adverse events (occurred since previous visit) recording.

If Visit 2 is anticipated of one day (Day 13) or postponed of 1 day (Day 15), any attempt will be done to fix the following Visit 3 so that 28 days of study and treatment are respected (i.e. if Visit 2 is on Day 13, then Visit 3 will be 15 days after Visit 2).

Visit 4 – End of treatment and end of study (Day 42 ±2):

The following activities will be done at Visit 4:

- Physical examination, focused on skin examination
- IGA on dermatitis
- EASI Score
- Change in concomitant medications/treatments recording
- VAS for itching, burning, pain, pruritus
- DQLI questionnaire
- Diary compilation check with the subject for treatment adherence and collection
- Study product collection and accountability
- Subject global evaluation of performance
- Investigator global evaluation of performance
- Subject global acceptability evaluation on the study product
- Adverse events (occurred since previous visit) recording.

Any attempt will be done to fix the Visit 4 so that the study and treatment days are as minimum 40 and as maximum 42.

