## 3. Justification for the Design of the Clinical Investigation

Dermatitis is a skin inflammatory disease commonly spreading in a limited area of the body and characterized by reddening, itching and skin dryness of the affected epidermis [1]. Dermatitis is a condition that can interfere with social function, sleep and employment. Its persistence and accompanying pruritus may be stressful and frustrating for patients.

The most common types of dermatitis are contact dermatitis (CD) and atopic dermatitis (AD), also referred as atopic eczema, but also dermatitis caused by radiotherapy or solar radiations can occur. Only atopic dermatitis and contact dermatitis will be included in this clinical investigation.

The most common and best characterized type of eczema, **atopic dermatitis (AD)**, appears to be increasing in incidence [2]. AD pathogenesis is not completely known, even though the disease seems to be the result of genetic susceptibility, immune dysfunction and epidermal barrier dysfunction [3]: it has been hypothesized that patients with eczema have defects in the skin barrier that allows antigens to enter and trigger the stimulation of inflammatory cytokines [4,5]. AD is characterized by a red and

itchy rash most commonly located where the skin flexes (e.g. inside the elbows, behind the knees and the front of the neck).

Other common eczematous dermatoses are contact dermatitis (CD), particularly allergic contact dermatitis (ACD) and irritant contact dermatitis (ICD).

**Contact dermatitis (CD)** is a rash that occurs on areas of the body that have come into contact with substances that either irritate the skin or cause an allergic reaction. CD can be irritant contact dermatitis (ICD) or allergic contact dermatitis (ACD). ICD is provoked by handling water, detergents, solvents or harsh chemicals and by friction, while ACD is due to skin contact with substances that most people don't react to (most commonly nickel, perfume, rubber, hair dye or preservatives). CD is commonly characterized by skin becoming red, blistered, dry, scaly and cracked.

The first precaution in ICD and ACD is to avoid or limit the contact with substances that are irritant or generate the allergic reaction.

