Although the above-mentioned types of dermatitis are characterized by different etiological factors, a key issue of the clinical condition is the dysfunction of the epidermal barrier. An altered skin barrier is the initial step that starts the so-called "vicious circle" of atopic dermatitis, characterized by dryness, tendency to itching and scratching, risk of superinfections, inflammation, pain and sleep disturbances.

In order to support the resolution of epidermis damage in the case of any dermatitis, the principal approach is the induction and enhancement of skin barrier repair.

Some of the currently available treatments for dermatitis management forecast the topical application of drugs - such as corticosteroids or immunosuppressants - acting at reducing the underlying inflammation and hypersensitization of the epidermis, though they are related to some side effects resulting from the topical application [7,8,9,10, 11].

On the other hand, to effectively heal the skin barrier, TEWL (Trans Epidermal Water Loss) must be minimized and the skin must be protected from further contact with irritants, allergens and infectious organisms [12].

A number of clinical trials have shown that moisturizers lessen symptoms and signs of dermatitis, including pruritus, erythema and fissuring [13-15]. Most of the time, rash and itching are successfully treated within three weeks [16]. It is now widely accepted that the application of topical moisturizers, emollients and protective agents should be an integral part of the treatment of patients with atopic and contact dermatitis, and there is strong evidence that their use can reduce the need for pharmacologic intervention to treat disease flare-ups.

Moisturizers - including petrolatum, physiological lipid mixtures, and ceramide-dominant triple-physiologic lipid (ceramide:cholesterol:free fatty acids at a 3:1:1 molar ratio) - play critical roles in dermatitis management [17]. Their daily use is now universally recommended to improve clinical symptoms and enhance skin barrier function. Moreover, the barrier improvement deriving from the prolonged use of these products is particularly relevant, given that the long-term topical application of corticosteroids is not well-tolerated and also reduces skin barrier function and increases TEWL [18].

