#### **4. Risk and Benefits of the Investigational Device and Clinical Investigation**

To date a large variety of products for the treatment of eczematous dermatoses are available.

DermoRelizema ecofoam is a medical device that is CE marked and already in use to treat dermatitis symptoms such as itching, flushing and erythema. In this clinical investigation DermoRelizema ecofoam will be used in adult subjects with mild to moderate dermatitis, of any origin, and erythema, according its IFU.

DermoRelizema ecofoam will be recommended twice daily for 42 days ( $\pm 2$ ). The product's components are known to be safe and well tolerated, therefore no risk seems to be associated to DermoRelizema ecofoam use.

The only precaution for users is to avoid contact of the product with eyes and mucous membranes (if contact does occur rinse immediately with plenty of water).

Within the clinical investigation the subject will be provided with instructions on the personal hygiene to follow, in order to further improve skin care and safety.

No tests or invasive examinations are foreseen in this study that can increase the risk for participants.

In the light of the above, no additional risk arising from the participation to this clinical investigation can be envisioned.

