### 9.1.1 Baseline Values

Data and Measures collected at Visit 1, before any study treatment administration, are considered as baseline values.

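### Ecofoam and a hygiene regimen start together without a control: must the SAP redefine the treatment as the combination?

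*Protocol*

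**What the plan says.** Visit 1 combines screening, baseline and treatment start (Protocol 6.4.1). At that visit the IGA is scored, ecofoam is handed over and the hygiene instructions are given. SAP 9.1.1 fixes the baseline there: "Data and Measures collected at Visit 1, before any study treatment administration, are considered as baseline values".

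The hygiene instruction in Protocol 6.4.1 is that "throughout the treatment phase subjects will be required to avoid soap and use only the product DermoRelizema liporestitutive cleanser", together with a bathing routine. On other products, the same section says: "No additional creams, moisturizers, lotions or cleansers other than the product provided by the Investigator will be permitted". Protocol 6.2.2 puts the hygiene rule more softly: "The subject will be recommended not to use any other product for the personal hygiene than the one provided by the Investigator". Protocol 4 gives its purpose: "the subject will be provided with instructions on the personal hygiene to follow, in order to further improve skin care and safety".

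On recording, Protocol 6.4.1 says that "on the diary each subject will record, at the end of each day, the study product applications performed". The compliance formula in SAP 11.3 and the variable list in SAP 9.1 likewise cover ecofoam applications and have no cleanser item.

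Protocol 5.1 and 6.1 name ecofoam alone in the objective and the treatment group. SAP 3.1, 4.1 and 4.2 do the same. Protocol 6.1 and SAP 4.1 both call the study uncontrolled.

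**The concern.** Two things change at the moment baseline is taken: the subject starts the foam, and also changes washing habits using a second product supplied for the study. With no control and no hygiene run-in, the data cannot separate the two, or separate either from the passage of time.

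The protocol does not treat the regimen as neutral. Besides the purpose given in its section 4, section 3 names detergents among the causes of irritant contact dermatitis and adds: "The first precaution in ICD and ACD is to avoid or limit the contact with substances that are irritant or generate the allergic reaction". The restriction on other creams might work the other way, since section 3 also says: "A number of clinical trials have shown that moisturizers lessen symptoms and signs of dermatitis, including pruritus, erythema and fissuring".

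A reader who saw only the SAP and its tables would not learn of any of this. The stated purpose is to confirm the performance of ecofoam, so a success proportion significantly above 50% could be credited to the foam when part of it came from avoiding soap.

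**Working it through.** **The plan's own figure.** Inputs from Protocol 7.1 and SAP 7: null proportion 0.50, alternative 0.75, two-sided 5% exact binomial test, 30 evaluable subjects, 25% dropout. The formula is P(X ≥ c | n, p) = Σ C(n,x) pˣ(1−p)ⁿ⁻ˣ, summed from x = c to n.

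- n = 30, c = 21: upper tail at 0.50 is 0.0214, two-sided 0.0428. With c = 20 the two-sided value is 0.0987, so 21 is the critical count.
- Power at 0.75: P(X ≥ 21 | 30, 0.75) = 0.8034. The stated 80% is reproduced.
- Enrolment: 30 / (1 − 0.25) = 40, also reproduced.
- If all 40 are evaluable, c = 27: upper tail 0.0192, two-sided 0.0385, power 0.8968.

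**What an inert foam could do.** The documents give no success rate without ecofoam, so the rates below are assumptions. Each entry is the chance of a significant result above 50% if the foam adds nothing.

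| Assumed success rate without ecofoam | n = 30 (≥ 21) | n = 40 (≥ 27) |
|---|---|---|
| 50% | 2.1% | 1.9% |
| 55% | 6.9% | 7.5% |
| 60% | 17.6% | 21.1% |
| 65% | 35.8% | 44.1% |
| 70% | 58.9% | 70.3% |
| 75% | 80.3% | 89.7% |

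The table shows why rejecting 50% does not establish an effect of the foam. It does not measure the hygiene regimen. The assumed rate pools natural course, regression to the mean, unblinded scoring and hygiene, and the same numbers would apply to any single-arm study of this size tested against 50%, with or without a cleanser.

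Read in reverse, the rows for 70, 65 and 60% would give the power if the restriction on moisturizers pulled the planned 75% down. That reading has no basis here: 75% is the alternative stated for this protocol, restriction included.

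**The restriction on other topicals.** Exclusion criteria 10 and 11 (Protocol 6.3.2) already bar topical medication for dermatitis for 14 days, and any topical product for dermatitis for 2 days, before treatment. For those products the restriction precedes baseline. Ordinary moisturizers may fall outside that wording, and 2 days is short. Even so, keeping other topicals out removes a competing explanation. Nor are subjects left without a moisturizing product: Protocol 3 says ecofoam contains glycerin, panthenol and hyaluronic acid and describes them as humectants.

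**SAP against protocol.** SAP 3.1 matches Protocol 5.1, and the treatment group in SAP 4.1 matches that in Protocol 6.1. Neither document claims an effect of ecofoam alone, and the primary endpoint is a change from baseline. If SAP 3.1 and 4.1 were rewritten to name a combined regimen, they would no longer match the protocol, which can be changed only by written amendment (Protocol 9).

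**What the rewrite would alter.** Critical counts, power, enrolment, populations, tests and data would all be unchanged.

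**The case for a change.** The best argument for acting is that the word *uncontrolled* is not enough. It warns that time and expectation are not separated; it does not tell a reader that a second product from the same range was used throughout. That is information about the intervention, and it is missing from the document that shapes the tables. The CE mark rested on literature (Protocol 3), so attribution to the foam is close to the purpose of the study, and a few sentences would cost little.

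Part of this stands. Improvement cannot be credited to ecofoam alone, and the report should say so. The supplied text describes no measure of cleanser adherence, although the eCRF and the diary form are not available, so it cannot be said that none was planned. *Recommended* in Protocol 6.2.2 and *required* in 6.4.1 do not agree and must be reconciled; the report should state which instruction subjects received.

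None of this reaches the analysis. The regimen is set out in Protocol 4, 6.2.2 and 6.4.1. SAP 6.2 ties the final analysis to the protocol as well as the SAP, and SAP 16.1 attaches the protocol to the report. Use of other treatments is recorded and listed (Protocol 6.2.2; SAP Listing 16.2.8), and protocol deviations are reviewed and tabulated (SAP 10.2). Giving all subjects the same hygiene rules is a fair design choice in a single-arm study.

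**Conclusion.** No change to the plan follows. The limit on attribution is real, but it belongs to the uncontrolled design, which both documents declare, and the regimen is disclosed in the protocol. Naming a combined treatment in the SAP would add description without altering any result, and would separate the SAP from the protocol it follows.

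The numerical effect on the plan is nil: 21 of 30 or 27 of 40 successes are still needed, and power at 75% stays at 80.3% or 89.7%. The size and direction of the regimen's own effect are unknown. The illustrative range, from 2.1% at an assumed 50% to 58.9% at an assumed 70% with 30 subjects, concerns everything other than the foam taken together.

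What remains is a minor reporting matter: a sentence among the limitations of the clinical report, and a wording mismatch between two protocol sections to reconcile. The conclusion assumes that the report describes the result as improvement from baseline under the study conditions and not as a controlled effect of ecofoam.
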